**Objectives and Endpoints**

Secondary Objectives	Secondary Endpoints
To characterize the PK of LY3316531 following IV and SC administration in healthy subjects	C max and AUC
To characterize the PK of LY3316531 following IV administration in patients with psoriasis	
Exploratory Objectives	Exploratory Endpoints
To evaluate the injection tolerance after SC administration of LY3316531	Pain scale scores and severity of ISR
To evaluate the formation of ADA to LY3316531	Presence of ADA against LY3316531
To evaluate the PD response (target engagement) of LY3316531 using total CGRP	Summary of total CGRP concentrations for each cohort and study time point
CCI	CCI
To evaluate patient-reported outcomes, including measurement of disease activity of LY3316531 in patients with psoriasis	Summary (mean, standard deviation, median, minimum, and maximum) of absolute percentage change from baseline for all of each cohort and overall for each sample day/time combination and maximum over the entire study for the patient's global assessment
To evaluate relationships between LY3316531 exposure and PD and clinical activity measures and safety endpoints	Graphical and model-based summaries of relationships between LY3316531 exposure and total CGRP, CCI , PASI, sPGA, ECGs, and safety endpoints of interest

Abbreviations: ADA = antidrug antibody; AUC = area under the concentration versus time curve; CGRP = calcitonin gene-related peptide; Cmax = maximum observed drug concentration; ECG = electrocardiogram; IL = interleukin; ISR = injection-site reaction; IV = intravenous; PASI = Psoriasis Area and Severity Index; PD = pharmacodynamics; PK = pharmacokinetics; SAE = serious adverse event; SC = subcutaneous; sPGA = static Physician Global Assessment; TEAE = treatment-emergent adverse event.

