#### **6.3.1. Meals and Dietary Restrictions**

Subjects should not eat after midnight during the night before study drug administration. Water is permitted. Subjects may eat breakfast approximately 2 hours postdose. A normal diet may be consumed at all other times during the study.

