### **9.5.1. Bioanalysis**

Samples will be analyzed at a laboratory approved by the sponsor and stored at a facility designated by the sponsor.

Serum concentrations of LY3316531 will be assayed using validated enzyme-linked immunosorbent assay methods. Analyses of samples collected from subjects who received placebo are not planned.

Bioanalytical samples collected to measure study drug concentrations will be retained for a maximum of 1 year following last subject visit for the study. During this time, samples remaining after the bioanalyses may be used for exploratory metabolism studies or exploratory analyses such as bioanalytical assay validation or cross-validation exercises.

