##### **10.3.3.1. Pharmacokinetic/Pharmacodynamic Analyses**

Analyses of the relationship between LY3316531 exposure and efficacy endpoints collected in Part C (such as PASI score, sPGA, and BSA) will be investigated initially using graphical methods. Modeling approaches that use a simple direct response relationship (using AUC) or longitudinal models that link the time course of LY3316531 concentrations to the time course of response may be explored.

Analyses of the relationship between LY3316531 exposure and total CGRP serum concentrations will also be conducted using graphical- and model-based approaches. Additional PD endpoints and safety endpoints may be explored for exposure-response relationships if warranted upon review of the data.

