### **APP.6.1. Part A (SAD in Healthy Subjects)**

Visit	Week	Day Relative to LY/PL Treatment	PK Sampling Time IV Dosing a	PK Sampling Time SC Dosing a	Immunogenicity Sampling a	ECG b
2	0	1	Predose	Predose	Predose	Predose
2	0	1	End of infusion c	NA	NA	End of infusion c
2	0	1	2 h after start of infusion	NA	NA	NA
2	0	1	6 h after start of infusion	6 h post-injection	NA	6 h after SC injection or start of infusion
2	0	1	NA	NA	NA	12 h after start of infusion
2	0	2	24 h after start of infusion	24 h post-injection	NA	24 h after SC injection or start of infusion
3	0	4 ± 1 day	Any time during day	Any time during day	NA	NA
4	1	8 ± 1 day	Any time during day	Any time during day	NA	Any time during day
5	1	11 ± 1 day	NA	Any time during day	NA	NA
6	2	15 ± 2 days	Any time during day	Any time during day	Any time during day	Any time during day
7	3	22 ± 2 days	Any time during day	Any time during day	NA	NA
8	4	29 ± 2 days	Any time during day	Any time during day	Any time during day	NA
9	6	43 ± 3 days	Any time during day	Any time during day	NA	Any time during day
10	8	57 ± 3 days	Any time during day	Any time during day	NA	NA
11	10	71 ± 3 day	Any time during day	Any time during day	NA	NA
12	12	85 ± 3 days	Any time during day	Any time during day	Any time during day d	Any time during day
ED		ED	Any time during day	Any time during day	Any time during day d	Any time during day

Abbreviations: ADA = antidrug antibody; ECG = electrocardiogram; ED = early discontinuation; h = hour(s); IV = intravenous; LY = LY3316531; PL = Placebo; NA = not applicable (no sampling needed at this time point); PK = pharmacokinetic; SC = subcutaneous; TE = treatment emergent.

a In the event of drug hypersensitivity reactions (immediate or non-immediate), up to 3 additional samples will be collected each for pharmacokinetics and immunogenicity as close to the onset of the reaction event as possible, at the resolution of the event, and 30 days following the event.

- b ECG measurement should occur prior to the blood draw.
- c Required for subjects receiving intravenous dosing only. ECGs (and vital signs) should be measured within 5 minutes prior to the end of infusion and PK samples as soon as possible after the infusion is completed

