9.5.5 Electrocardiogram (ECG)

The ECG data will be obtained directly from the 12-lead ECG traces. These data include the PR, QT, QTcB intervals, QRS duration and heart rate, where QTcB is the QT interval corrected using Bazett's formula. In addition, QTcF (the QT interval corrected using Fridericia's formula) will be calculated as follows:

$$QTcF = \frac{QT}{\sqrt[3]{(60/HR)}}$$

The ECG data will be summarized by treatment together with changes from baseline, where baseline is defined as Day 1 predose. Figures of mean ECG data and mean changes from baseline will be presented by treatment. The frequency of subjects with a maximum increase from baseline in QTcB and QTcF interval will be summarized for each treatment according to the following categories: >30 ms and >60 ms. In addition, the frequency of subjects with QTcB and QTcF postdose values, according to the following categories: >450 ms, >480 ms and >500 ms, will be summarized by treatment.

A plasma LY3316531 concentration-QT analysis will be performed to assess the changes from baseline (Day 1 predose) QTcF interval relative to plasma LY3316531 concentrations across all active treatments. The change from baseline adjustment will be based on individual subject's Day 1 predose value. The analysis will be performed by plotting change from baseline QTcF against LY3316531 concentrations, including all post Day 1 dosing timepoints. The plot will be produced separately for parts A, B, and C of the study. Each plot will include a simple linear regression.

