9.5.15 Safety and Tolerability Statistical Methodology

No inferential statistical analyses are planned.

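### The Part A concentration-QTcF line has no time-point or placebo term, so a non-drug QTcF shift that differs between visits enters its slope

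*SAP*

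**What the plan says.** SAP 9.5.5 sets out a concentration-QT analysis of change from Day 1 predose QTcF "relative to plasma LY3316531 concentrations across all active treatments". It uses every time point after Day 1 dosing, gives one plot for each of Parts A, B and C, and adds that "Each plot will include a simple linear regression". Concentration is the only predictor.

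Conditions at the ECGs differ by visit:
- Protocol 5.1 has subjects fast overnight before dosing.
- Protocol 6.3.1 then says "Subjects may eat breakfast approximately 2 hours postdose. A normal diet may be consumed at all other times during the study".
- Protocol APP.6.1 schedules the Day 8, 15, 43 and 85 ECGs as "Any time during day".

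Placebo subjects follow the same ECG schedule, but Protocol 9.5.1 says of drug assays: "Analyses of samples collected from subjects who received placebo are not planned". SAP section 6 makes pooled placebo a treatment group within each part, so its ECG changes are summarised beside the active doses, outside the regression.

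SAP 9.5.15 states: "No inferential statistical analyses are planned". Protocol Table FFAA.4.1 includes ECGs among the exploratory endpoints for model-based exposure summaries, but no section specifies such a model. Protocol 10.3.3.1 leaves it open: "Additional PD endpoints and safety endpoints may be explored for exposure-response relationships if warranted upon review of the data".

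**The concern.** After an IV dose, time and concentration are tied together: the early ECGs carry the high concentrations and the late ones the low. If QTcF moves for a non-drug reason at some visits and not others, a regression on concentration alone attributes part of that movement to drug. The wide dose range does not prevent this, because the high-dose cohorts at early times have most of the leverage.

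Two limits apply. A shift common to all postdose visits goes into the intercept and leaves the slope unchanged. Random variation in clock time adds noise, not bias. Only a systematic shift that differs between visits matters.

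At stake is how the plot is read. In a first-in-human study, its slope could hide or mimic a few milliseconds of drug effect, while the placebo ECGs that would help separate the two in Part A are already collected.

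**Working it through.** The plan states no slope or precision for this analysis, so there is no figure to reproduce. One check of the PK anchors in Table FFAA.5.2: 436 × (2000/3) / 672 h = 432.5, against the stated Cav,ss of 432.

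**Inputs from the documents (Part A)**
- Active: 3+3+6+6+6+6 = 30 IV and 6 SC. Placebo: 1+1+2+2+2+2 = 10.
- ECG times with a PK sample (APP.6.1): end of infusion (IV only), 6 h, 24 h, Days 8, 15, 43 and 85. The 12 h ECG has no PK sample. Pairs: 30×7 + 6×6 = 246.
- Cmax: 1.8/3 = 0.6 µg/mL per mg, so 1200 µg/mL at 2000 mg. AUC at 3 mg: 436 µg·h/mL. Half-life: 2 to 3 weeks (Protocol 5.4).

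**Assumptions**
- A -5 ms shift and no drug effect. Results scale linearly with the shift.
- The end-of-infusion ECG is before breakfast and unshifted.
- Fed status at 24 h is not stated, so the 24 h ECG is taken both ways.

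**Formula**

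Slope bias = Σ(C − C̄)·s(t) / Σ(C − C̄)², multiplied by 1200 for the effect at the predicted top-dose Cmax.

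**One case in full.** Dose-proportional two-phase PK matched to Cmax 1.8 and AUC 436; terminal half-life 14 days, distribution half-life 1 day; SC bioavailability 0.6, absorption half-life 3 days.
- Mean concentrations at the seven times: 390.85 (30 pairs), then 299.35, 235.71, 114.78, 80.80, 20.25 and 2.53 (36 pairs each).
- C̄ = (30×390.85 + 36×753.42)/246 = 157.92. Σ(C − C̄)² = 20,125,184.
- Summed deviations: end of infusion 30×232.93 = 6,988; 6 h 36×141.43 = 5,091; 24 h 36×77.79 = 2,800; Days 8 to 85 together -14,879.
- 6 h only: -5×5,091/20,125,184×1200 = -1.52 ms.
- 6 h and Days 8 to 85: -5×(5,091 − 14,879)/20,125,184×1200 = +2.92 ms.
- The 24 h ECG as well: -5×(5,091 + 2,800 − 14,879)/20,125,184×1200 = +2.08 ms.
- All seven times: 0.

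**Range over PK settings.** One-compartment with half-life 14, 17.5 or 21 days, or two-phase also matching Cmax,ss 1428 with terminal half-life 17.5 or 21 days; PK CV 0 or 30%; SC bioavailability 0.7.

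| ECGs shifted by -5 ms | Change in the line at 1200 µg/mL |
|---|---|
| 6 h only | -0.7 to -1.6 ms |
| 6 h, Days 8 to 85 | +1.6 to +3.1 ms |
| 6 h, 24 h, Days 8 to 85 | +0.9 to +2.8 ms |

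Redrawing the 30% PK variation moves the first two lower ends to -0.6 and +1.4 ms. A true +5 ms effect would be drawn as 5 − 1.6 = 3.4 to 5 − 0.7 = 4.3 ms, or as 5 + 0.9 = 5.9 to 5 + 3.1 = 8.1 ms.

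**Which term removes it.** With a categorical time-point factor the slope bias is 0 in every case, with or without placebo. Placebo at concentration zero without the time factor leaves -1.43 of the -1.52 ms in the case above. With a random subject intercept as well, -1.2 to -3.7 ms remains for the 6 h shift. Given the time factor, leaving placebo out makes the slope SD about 5 to 8% larger.

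If the placebo shift is half or double the active shift, the time-plus-placebo model leaves 0.2 to 0.6 ms in the 6 h case and at most 0.5 ms in the case including 24 h.

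**Precision.** By generalised least squares with within-subject correlation 0.3 to 0.7, the model's slope SD is 0.53 to 0.91 times that of the planned line.

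**Simulation.** 500 mixed-model fits per case; shift mean -5, SD 3 ms; total SD 7 ms; correlation 0.5; one-compartment and two-phase PK, both 17.5 days.

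| Shift | Planned line | Mixed model |
|---|---|---|
| 6 h | -0.8 and -1.6 ms (SD 2.5, 3.0) | -0.1 and -0.1 ms (SD 1.8, 2.3) |
| 6 h, 24 h, Days 8 to 85 | +0.8 and +2.4 ms | -0.1 and -0.1 ms (SD 1.9, 2.4) |

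The 90% CI covers in 0.90 to 0.91 of fits.

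**Part B Cohort 1** (15 ECG-PK times, same -5 ms): -0.1 to -0.8 ms for a Day 1 6 h shift; +0.3 to +3.5 ms if the outpatient ECGs shift too.

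**The case against.** The strongest reply is that this is a descriptive plot resting on an assumed artefact. No section says that a meal or clock time moves QTcF. The -5 ms is a choice, and the direction of the bias depends on which ECGs are taken to shift. In the simulation, the 6 h shift moves the planned line by about half its own SD or less. All of that is true. It limits the consequence, but it does not remove the slope's dependence on visit effects.

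The one-compartment settings also disagree with Table FFAA.5.2. They imply a 3 mg AUC of 873 to 1309 rather than 436, and a Cmax,ss of 1600 to 1990 rather than 1428. That is correct, but those settings supply only the low ends. Settings that match the table give about -1.5 to -1.6, +2.8 to +3.1 and +2.0 to +2.8 ms, so the quoted ranges understate the effect if anything.

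The by-treatment ECG summaries show the placebo time course. SAP 9.4.2 assigns PK-PD work to the sponsor, and SAP section 3 permits supplementary analyses. This is partial cover: a pooled slope cannot be corrected by eye from separate mean plots, and exposure-safety modelling remains optional.

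Finally, the time factor does nearly all of the bias removal, and a mixed model with a CI goes beyond a descriptive plot. The first part stands, and the fix treats the time factor as essential. On the second, a 90% CI is reported as estimation, with no test or threshold attached.

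**Conclusion.** The concern holds. As specified, the Part A slope mixes any drug effect with visit effects that follow the fall in concentration, and no other section of either document corrects it. For each assumed 5 ms of visit-specific shift, the error at 1200 µg/mL is roughly 1 to 3 ms, in either direction. This rests on the assumed shift and its timing, on predicted PK, and on dose-proportional concentrations. A uniform shift would do no harm. No endpoint, dose decision or threshold uses the slope, so this is an improvement worth making, not a flaw that threatens the trial's conclusions. Confidence is medium, because the documents give no size for the shift.

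**What to change.** **Part A.** In SAP 9.5.5, replace the simple regression with a linear mixed model of change in QTcF on concentration, nominal time point (categorical) and centred baseline QTcF, with a random subject intercept. Include the pooled-placebo subjects at concentration zero. Report the predicted placebo-corrected change at the mean Cmax of the top dose with a 90% CI, labelled descriptive.

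**Part B.** Show the same model as supportive beside the planned line. Cohort 1 has 6 active and 2 placebo subjects and, unless Part A shows changes, single locally stored ECGs (Protocol 9.4.3). The model's slope SD there is 0.7 to 1.35 times that of the planned line with 30% PK CV, and 1.5 to 1.95 times if PK does not vary.

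**Part C.** There is no placebo, and time cannot be separated from concentration. Keep the plot, state that it is not corrected for time, and read it alongside Part A.

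**Cost.** SAP wording and one programmed model. Setting placebo concentrations to zero needs no assay, and no ECG, sample or visit is added.

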9.5.9 Immunogenicity

Immunogenicity data will be listed and frequency tables will be presented. The frequency of treatment-emergent ADAs will also be calculated. Treatment-emergent ADAs are those that are induced or boosted by exposure to study drug, with a 4-fold increase in titer compared to baseline if ADAs were detected at baseline or a titer 2-fold greater than the minimum required dilution (1:40) if no ADAs were detected at baseline.

To show the association of treatment-emergent ADAs with AEs, the frequency of treatment-emergent ADAs will be presented by MedDRA preferred term. Relationship between the presence of antibodies and the PK parameters of LY3316531 may be assessed graphically.

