#### ***10.3.4. Evaluation of Immunogenicity***

The frequency and percentage of patients/subjects with baseline ADA, with ADA anytime postbaseline, and/or with TE ADA to LY3316531 will be tabulated. For patients/subjects who are ADA negative at baseline, TE ADAs are defined as those with a titer 2-fold (1 dilution) greater than the minimum required dilution of the assay. For patients/subjects who are ADA positive at baseline, TE ADAs are defined as those with a 4-fold (2 dilutions) increase in titer compared to baseline. For the patients with TE ADA, the distribution of maximum titers will be described. The frequency and percentage of patients with neutralizing antibodies may also be tabulated for patients with TE ADA.

The relationship between the presence of antibodies and the PK parameters and PD response including safety to LY3316531 may be assessed.

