7. SAMPLE SIZE JUSTIFICATION

The sample size for each cohort is customary for first-in-human studies in which formal power analyses are not necessary to address the objectives associated with safety, tolerability, PK, and/or PD assessments. Approximately 86 patients/subjects are planned for enrollment; however, up to 102 subjects may be enrolled to allow for replacement of subjects and any additional dose cohorts (Parts A, B, and C).

Subjects/patients who withdraw from the study before completing the Day 57 (Part A) or Day 85 (Parts B and C) assessment may be replaced if necessary to have the planned number of subjects/patients complete a dose cohort. A replacement subject/patient will be assigned the same treatment as the subject/patient he or she replaces (Parts A, B, and C).

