9.5 Safety and Tolerability Assessments

9.5.1 Adverse events

Where changes in severity are recorded in the Case Report Form (CRF), each separate severity of the adverse event (AE) will be reported in the listings, only the most severe will be used in the summary tables. A pre-existing condition is defined as an AE that starts before the subject has provided written informed consent and is ongoing at consent. A non-treatment emergent AE is defined as an AE which starts after informed consent but prior to dosing. A treatment-emergent AE is defined as an AE which occurs postdose or which is present prior to dosing and becomes more severe postdose. AEs by day of onset will be presented for Part B.

All AEs will be listed. Treatment-emergent AEs will be summarized by treatment, severity and relationship to the study drug. The frequency (the number of AEs, the number of subjects experiencing an AE and the percentage of subjects experiencing an AE) of treatment-emergent AEs will be summarized by treatment, Medical Dictionary for Regulatory Activities (MedDRA) version 20.0 system organ class and preferred term. The summary and frequency AE tables will be presented for all causalities and those considered related to the study drug. Any serious AEs will be tabulated.

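### SAP 9.5.9 sets out to show how ADAs relate to AEs, but its one planned display has no ADA-negative comparison and no time order

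*SAP*

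**What the plan says.** SAP 9.5.9 states an aim and one display to meet it: "To show the association of treatment-emergent ADAs with AEs, the frequency of treatment-emergent ADAs will be presented by MedDRA preferred term". It gives no unit, no denominator, no ADA-negative group and no rule on whether the event must follow the antibody. The same section adds that "Immunogenicity data will be listed and frequency tables will be presented" and that "The frequency of treatment-emergent ADAs will also be calculated".

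Adverse events are handled in SAP 9.5.1. The frequency of treatment-emergent AEs "will be summarized by treatment, Medical Dictionary for Regulatory Activities (MedDRA) version 20.0 system organ class and preferred term", so the split is by treatment and not by ADA status. On timing it says "AEs by day of onset will be presented for Part B", with no link to ADA dates and nothing for Parts A and C.

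Protocol 10.3.4 does not fill the gap. It says only that "The relationship between the presence of antibodies and the PK parameters and PD response including safety to LY3316531 may be assessed", with no method, comparator or time window. SAP 9.5.15 confirms that safety is descriptive: "No inferential statistical analyses are planned".

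**The concern.** An association between ADA and an AE is a contrast: how often the event occurs in TE-ADA-positive subjects against how often it occurs in TE-ADA-negative subjects given the same drug. Counting positive subjects under each preferred term gives one part of that contrast. If ADA has nothing to do with AEs, such a table simply repeats the overall ADA rate under each term, with wide scatter where few subjects have the term.

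Time order is the second gap. An antibody cannot explain an event that came before it, yet the display has no means of separating events before seroconversion from those after.

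This is the only firmly planned analysis of ADA against AEs for a new bispecific antibody. A reader of the study report could take a chance cluster for a signal, or miss a real excess of late events in positive subjects.

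**Working it through.** **Denominators.** SAP section 7 says "Approximately 86 patients/subjects are planned for enrollment". From the cohort table (SAP Table 1):
- Part A LY3316531: 3 + 3 + 6 + 6 + 6 + 6 + 6 = 36; placebo: 1 + 1 + 2 + 2 + 0 + 2 + 2 = 10.
- Part B: 12 LY3316531 and 4 placebo. Part C: 24 LY3316531.
- Total: 36 + 10 + 12 + 4 + 24 = 86, as stated. The stated maximum also agrees: 52 + 20 + 30 = 102.

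The documents give no ADA rate or AE rate. Every such rate below is an assumption.

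**One entry, several associations.** Suppose a term occurs in 6 of the 36 Part A LY3316531 subjects and 4 of those 6 are TE-ADA positive. With m positive overall, AE risk is 4/m in positives and 2/(36 − m) in negatives.

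| m positive of 36 | AE risk, ADA-positive | AE risk, ADA-negative | Risk ratio | Fisher two-sided p |
|---|---|---|---|---|
| 6 | 4/6 = 66.7% | 2/30 = 6.7% | 10.0 | 0.003 |
| 12 | 4/12 = 33.3% | 2/24 = 8.3% | 4.0 | 0.15 |
| 18 | 4/18 = 22.2% | 2/18 = 11.1% | 2.0 | 0.66 |
| 24 | 4/24 = 16.7% | 2/12 = 16.7% | 1.0 | 1.0 |
| 30 | 4/30 = 13.3% | 2/6 = 33.3% | 0.4 | 0.26 |

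The entry 4 of 6 is the same in every row.

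**Entries that arise by chance.** With ADA and AE independent, the expected number of ADA-positive subjects with the term is 36 × (ADA rate) × (AE rate). This runs from 36 × 0.1 × 0.1 = 0.36 to 36 × 0.7 × 0.3 = 7.56. The chance of at least one is 1 − (1 − product)^36, from 30% to nearly 100%.

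For rare terms, at an assumed 40% ADA rate and no association:
- Term in 2 subjects, at least one positive: 1 − 0.6² = 64%.
- Term in 3 subjects, at least two positive: 3 × 0.4² × 0.6 + 0.4³ = 35%.
- At a 20% ADA rate the two figures are 36% and 10%.

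**Placebo in the comparison.** SAP section 8 bases safety analyses on all enrolled subjects, which includes placebo. Assume no TE-ADA on placebo, AE rates of 30% on LY3316531 and 10% on placebo, and no ADA effect within LY3316531. With ADA rate q, AE risk in the mixed negative group is [36(1 − q) × 0.3 + 10 × 0.1] / [36(1 − q) + 10]. At q = 0.5 this is 6.4/28 = 22.9%, a crude risk ratio of 0.3/0.229 = 1.31. At q = 0.3 and 0.7 the ratio is 1.23 and 1.47. The contrast therefore belongs within LY3316531-treated subjects.

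**Timing.** Scheduled post-baseline ADA samples (Protocol Appendix 6) are:
- Part A: Days 15, 29 and 85.
- Part B: Days 15, 29, 57, 85 and 141, with those on Days 29 and 57 taken before the dose.
- Part C: Days 15, 29, 85 and 113, plus Weeks 26 and 52 in extended follow-up.

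In Part A, a subject with a headache on Day 1 and a first positive sample on Day 85 would count under ADA for headache. In Part B, the predose samples could place ADA status before the second and third infusions, but the display does not use them.

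**The case against.** The strongest reply is that the comparison can be recovered. SAP 9.5.9 also plans the overall TE-ADA frequency, and SAP 9.5.1 plans subject counts per preferred term. In the example, 4/6 = 66.7% set against 24/36 = 66.7% overall shows no association; set against 6/36 = 16.7% it shows a strong one. This stands in part. A reader might infer that the plan cannot show an association at all, and the documents do not support that. What remains is that the SAP does not say the tables share a population, treatment grouping and denominator. Reconstruction also gives no time order; that would have to come from listings.

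The layout may be fuller than the sentence suggests. SAP section 3 puts table detail in a shell document that is not among the documents reviewed, and SAP 9.1 requires counts and percentages for categorical data. But a percentage among subjects with a term still gives no AE risk in ADA-negative subjects, and the SAP text should state the comparator.

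On timing, a reader might infer that every AE in the first 14 days precedes any sample that could show a TE-ADA. That is wrong. Protocol 9.6.2 requires extra ADA samples near the onset of a hypersensitivity reaction, at its resolution and 30 days later. The Day 15 visit window opens on Day 13, and early discontinuation has its own sample. The timing gap concerns mainly other AEs.

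Finally, ADA formation is an exploratory objective, no inference is planned, numbers are small and subject-level data are listed. All true. Even 18 versus 18 subjects at 30% versus 10% would have about 32% power at two-sided 0.05. This limits the importance of the point and means that the remedy must stay descriptive.

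**Conclusion.** The point holds for the display as specified. Taken alone, TE-ADA frequency by preferred term does not determine the direction of an association: in the worked example one entry fits risk ratios from 0.4 to 10. It can also place under ADA events that came before any antibody. No other firm analysis in the SAP or protocol supplies the ADA-negative comparison or the time order.

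The consequence is modest. A reader might infer a threat to the primary safety objective, but the primary endpoint is incidence of AEs, TEAEs and SAEs, which is reported independently of this table. The change is worth making because the SAP claims to show an association and a standard table from data already collected would do so better.

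The result rests on reading the SAP sentence as a count of ADA-positive subjects within each term, which is the natural reading but is not stated, and on illustrative ADA and AE rates. An added column will not cure small-number noise.

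**What to change.** Replace the association sentence in SAP 9.5.9 with the following:
- TEAE incidence by preferred term, with denominators, in TE-ADA-positive versus TE-ADA-negative LY3316531-treated subjects, by study part. Show placebo separately. Leave cohort to the listings, because 3 to 8 active subjects per cohort are too few to split further.
- Separate rows for hypersensitivity, infusion and injection-site reactions.
- For TE-ADA-positive subjects, AE onset shown descriptively as before the last negative sample, between the last negative and first positive sample, or after the first positive sample. Use the event-driven hypersensitivity samples where taken.
- AEs before the first positive sample stay in the main comparison.

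Restricting positive subjects to AEs after the first positive sample is tempting but should be avoided. It treats detection as onset: Part A has no scheduled ADA sample between Days 29 and 85, so an antibody arising on Day 35 with an AE on Day 50 would be filed as AE first. It would also compare a short window in positive subjects with full follow-up in negative subjects.

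The cost is one SAP sentence and one re-shaped table from data already collected, with no new visits, samples or subjects. The downside is sparse cells, so the table should be labelled descriptive only.
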